2.1 Names of Investigational Devices

The FARAPULSE Endocardial Multi Ablation System is comprised of the following devices:

- FARAWAVE Endocardial Ablation Catheter
- FARAFLEX Endocardial Ablation Catheter
- FARASTAR Endocardial Generator System
- FARADRIVE Deflectable Sheath.

2.2 Intended Use

The FARAPULSE Endocardial Multi Ablation System is indicated for the treatment of drug refractory, recurrent, symptomatic persistent atrial fibrillation.

The FARAFLEX Endocardial Ablation Catheter is used as an adjunctive device in the endocardial treatment of persistent atrial fibrillation with the following intended uses:

- Gap ablation to complete electrical isolation of the pulmonary veins,
- Focal ablation of cardiac arrhythmias, and
- Creation of ablation line between the inferior vena cava and the tricuspid valve.

2.3 Classification

The FARAWAVE Endocardial Ablation Catheter and FARAFLEX Endocardial Ablation Catheter are classified as Class III medical devices. Per MDD 93/42/EEC Annex IX Rule 6 applies to the ablation catheters, which defines the catheters as surgically invasive devices intended for transient use (<60 min) that specifically controls, diagnoses, monitors or corrects a defect of the heart or of the central circulatory system through direct contact with these parts of the body.

The FARASTAR Endocardial Generator System is classified as a Class IIb medical device. Per MDD 93/42/EEC Annex IX Rule 9 applies to the generator system, which defines it as an active therapeutic device that is intended to administer or exchange energy to and from the human body in a potentially hazardous way, taking account of the nature, the density and the site of application of the energy.

The FARADRIVE Deflectable Sheath is classified as a Class III medical device. Per MDD 93/42/EEC Annex IX Rule 6 applies to the Deflectable Sheath System, which defines it as a surgically invasive device intended for transient use (<60 min) that specifically controls, diagnoses, monitors or corrects a defect of the heart or of the central circulatory system through direct contact with these parts of the body.

2.4 FARAPULSE Endocardial Multi Ablation System

The FARAPULSE Endocardial Multi Ablation System used in the proposed clinical investigation consists of the FARAWAVE Endocardial Ablation Catheter, the FARAFLEX Endocardial Ablation Catheter, the FARASTAR Endocardial Generator System, and the FARADRIVE Deflectable Sheath. These components, sub-components and model numbers are listed in **Table 1**.

Table 1. FARAPULSE Endocardial Multi Ablation System – Components

[figure not shown]
Component	Sub Components	Model Numbers
FARAWAVE Endocardial Ablation Catheter	1. Ablation Catheter (31 mm or 35 mm fully deployed diameter) 2. Extension Cable	40T401 (31 mm) and 40T404 (35 mm) 40T407 (extension cable)
FARAFLEX Endocardial Ablation Catheter (adjunctive device)	1. Ablation Catheter (17 mm fully deployed diameter) 2. Extension Cable	40T405 (catheter) 40T406 (extension cable)
FARASTAR Endocardial Generator System	1. Pulsed Electric Field Generator (PEFG) 2. Two Coaxial Cables 3. Pace Filter Box 4. Two Catheter Switch Boxes	60T401
FARADRIVE Deflectable Sheath (or commercially available CE Marked Deflectable Sheath System such as the CE Marked Oscar Destino™ Twist UniDirectional Deflectable Guiding Sheath)*	1. Sheath 2. Dilator	20T401

During the course of the investigation certain CE Marked medical devices may be used in conjunction with the FARAPULSE Endocardial Multi Ablation System. These are listed in **Table 2**.

Table 2. CE Marked Devices Utilized in Conjunction with FARAPULSE System

CE Marked Devices That May be Used in Conjunction with FARAPULSE Endocardial Multi Ablation System
*Oscor Destino™ Twist UniDirectional Deflectable Guiding Sheath
St. Jude BRK 98cm Transseptal Needle
MicroPace StimCor Cardiac Stimulator

A schematic of the FARAPULSE Endocardial Multi Ablation System is depicted in **Figure 1** following.

Note: Blue dotted box shows the sterile, single-use components of the system

Figure 1. FARAPULSE Endocardial Multi Ablation System Components

2.4.1 FARAWAVE Endocardial Ablation Catheter System

The FARAWAVE Endocardial Ablation Catheter System consists of two (2) components: Ablation Catheter and Extension Cable, which are used together. Both components are sterile and single use only.

The ablation catheter is offered in two different sizes: 31 mm (REF 40T401) and 35mm (REF 40T404) deployed diameters, to accommodate varying pulmonary vein anatomy. Selection of either catheter will be at the investigator's discretion.

The Ablation Catheter is a multi-electrode catheter that connects electrically to the Endocardial Generator System. It consists of a multi-electrode ablation catheter with electrodes arranged on splines. The Ablation Catheter consists of a distal section with five splines that deploy into a basket-shaped configuration or flower-shaped configuration with five petals, a shaft section, and a proximal handle with a manually operated deployment control (Figure 2), which depicts a fully deployed distal flower-shaped configuration.

[figure not shown]

Figure 2. FARAWAVE Endocardial Ablation Catheter

Each spline has a single electrode that is separately wired to facilitate connection to a mapping or recording system (this is an optional feature offered to the user). The handle includes a flush port for saline infusion, a deployment control knob with a guidewire lumen hub that can be connected to a hemostasis valve, and a cable with connectors. The catheter connectors connect to an Extension cable (part of the Endocardial Ablation Catheter System) with numbered connectors on each of its ends. These connect to the multi-channel FARASTAR Endocardial Generator. The Pulsed Electric Field energy is delivered via the FARASTAR Endocardial Generator over the set of ablation catheter electrodes. The Extension Cable is a single-use sterile cable that provides additional cable length to connect to the FARASTAR Endocardial Generator.

Additional details are provided in the IFU LBL0195 for the specific use and procedural steps of the FARAWAVE Endocardial Ablation Catheter.

2.4.2 FARAFLEX Endocardial Ablation Catheter

The FARAFLEX Endocardial Ablation Catheter is a multi-electrode unidirectional, deflectable percutaneous catheter that connects to the FARASTAR Endocardial Generator and is designed to deliver PEF energy from the Endocardial Generator for cardiac tissue ablation. The FARAFLEX Endocardial Ablation Catheter is an adjunctive catheter designed to create smaller focal-type lesions for the following indications for use:

- Gap ablation to complete electrical isolation of the pulmonary veins,
- Focal ablation of cardiac arrhythmias, and
- Creation of ablation line between the inferior vena cava and the tricuspid valve.

The catheter consists of the following major sections: 1) distal section with electrodes arranged on four (4) splines, 2) catheter shaft, and 3) proximal handle with manually operated deflection and deployment controls, flush port, and connector. **Figure 3** depicts a deployed FARAFLEX Endocardial Ablation Catheter.

[figure not shown]

Figure 3. FARAFLEX Endocardial Ablation Catheter

The catheter can be deployed into basket-shaped configurations to accommodate various anatomical locations. The ablation catheter is visible under fluoroscopy due to the presence of marker bands at the distal tip and proximal end of the splines, as well as electrodes on each of four (4) splines.

2.4.3 FARASTAR Endocardial Generator System

The FARASTAR Endocardial Generator System consists of the following components – Pulsed Electric Field Generator (PEFG), BNC Coaxial Cable (2 units), Pace Filter Box (1-2 units), and Switch Box (2 units). The Endocardial Generator System is designed to deliver PEF energy to endocardial sites in the heart via the FARAWAVE and FARAFLEX Endocardial Ablation Catheters and other compatible devices (refer to IFU LBL0195 and IFU LBL0565 for the specific use and procedural steps of the Endocardial Ablation Catheters, respectively; LBL0193 for the FARADRIVE Deflectable Sheath and LBL0198 for the FARASTAR Endocardial Generator System).

The FARASTAR Endocardial Generator is a 16-channel output unit that generates a pulsed voltage waveform that can be delivered to the ablation catheter electrodes. The FARASTAR Generator, while capable of operating between 1400V and 2100V, currently allows ablation energy in discrete user-selectable voltage settings between 1400V and 2000V.

As an input, a compatible cardiac stimulator unit for cardiac pacing is applied to the cardiac chambers via pacing catheters and to the FARASTAR Endocardial Generator with a coaxial cable to synchronize the application of therapeutic PEF energy to the actively paced heart. The physician confirms proper synchronization by actuating a

button on the FARASTAR Endocardial Generator user interface. The BNC Coaxial Cable is used to connect the generator to a commercially available compatible cardiac stimulator/pacing device.

Details regarding the generator are provided in the FARASTAR Endocardial Generator System User Manual LBL0198.

2.4.4 FARADRIVE Deflectable Sheath

The FARAWAVE Endocardial Ablation Catheter and FARAFLEX Endocardial Ablation Catheter are used with the FARADRIVE Deflectable Sheath or a compatible CE Marked Deflectable Sheath System (13F) such as the CE Marked Oscar Destino™ Twist UniDirectional Deflectable Guiding Sheath.

The FARADRIVE Deflectable Sheath consists of two (2) primary components: Deflectable Sheath and Dilator, which are used together. Both components are sterile and single use only.

The FARADRIVE Deflectable Sheath is comprised of a distal deflectable section and a shaft section which connect to the handle. The handle includes a knob to control the deflection of the distal tip and a flush port for infusion of saline or contrast. The Dilator is intended for insertion through the sheath lumen and includes a shaped tip for dilation for vascular or chamber access (**Figure 4**).

Figure 4. FARADRIVE Deflectable Sheath and Dilator

2.5 Device Accountability

The FARAPULSE Endocardial Multi Ablation System will be stored in a secure location and access will be controlled. Records will be maintained to document the physical location of inventory from shipment and removal from Sponsor or Contract Manufacture facility through use and / or return or disposal.

The site will be responsible for maintaining a Device Accountability Log provided by the Sponsor or its designated representative. At a minimum the following will be recorded: Date of receipt, FARAPULSE Endocardial Multi Ablation System

components identification number (Generator, Ablation Catheter and Deflectable Sheath lot and / or serial number), expiration date, date of use, subject unique identification code and date of disposal or return of the device.

If there is a product Device Deficiency / Malfunction or other need to return the system or system components to the Sponsor or Contract Manufacture, the Sponsor or designee should be contacted for safe product disposal and/ or return details. Appropriate CRF will be completed in the event of a Device Deficiency / Malfunction.

The Investigator is responsible for ensuring that the investigational devices are used only under the Investigator's supervision and are only used according to this protocol and any approved amendments. The Investigator will not supply an investigational device to any person not authorized to participate in the study. The Investigator shall document on the Case Report Forms (CRFs) the lot numbers and / or serial numbers of the devices used during each case.

2.6 Return of Devices

All unused investigational devices will be returned to the Study Sponsor or designee upon completion of the clinical study. Any investigational device that does not meet performance specifications will also be returned to the Study Sponsor or designee for analysis per company procedures. The Investigator or his/ her designated representative is responsible for device accountability and disposition of all used and unused devices. The Study Sponsor or its designated representative will conduct device reconciliation at the completion of subject enrollment or at the conclusion of the study.

3. Study Design

3.1 Study Objective

The objective of this safety and feasibility study is to assess whether the endocardial creation of electrically nonconductive lesions via PEF catheter ablation applied using the FARAPULSE Endocardial Multi Ablation System is a feasible and safe treatment for PersAF and associated AFL.

3.2 Study Overview

This is a prospective, multi-center, unblinded single arm safety and feasibility study. Subjects will undergo percutaneous PEF ablation for pulmonary vein isolation and at the clinical discretion of the investigator receive PEF ablation of additional arrhythmogenic locations. Subjects will be followed at 30 days, 75 days, 6 months and 12 months for adverse events, recurrence of arrhythmia after a 90-day Blanking Period and other relevant outcome measures.

3.3 Subject Confidentiality

Enrolled subjects will be assigned a unique, pseudo-anonymous identifier that will be used to maintain confidentiality of each subject's medical information. Subject names and other protected health information will not be captured on the CRFs. In addition, all patient identifiers except the unique pseudo-anonymous identifier should be redacted from any images or other data submitted from the participating site to the Sponsor or the Sponsor's designated reviewers for analysis. All information concerning subjects or their participation in this study will be considered confidential. Only the authorized Sponsor, designated representative personnel, designated consultants and regulatory agencies will have access to these confidential files.

3.4 Written Informed Consent

All subjects must provide written Informed Consent using the EC-approved ICF before undergoing any study related procedures.

Routine clinical evaluations that would be performed as part of the normal clinical care of patients may be performed prior to such consent and used as part of the screening assessment. If the subject is subsequently consented and enrolled in the study, the results of such evaluations may be used as study data.

Subjects cannot be asked to sign the ICF until the study has been fully approved by the institution's EC and by the CA, if applicable, and the Sponsor or their CRO representative has received and reviewed the EC-approved ICF. Subjects who meet the general entry criteria will be asked to sign an ICF as approved by the relevant regulatory authorities before any study-specific tests or procedures are performed.

The Investigator or a designated member of his / her staff should approach the subject to obtain written informed consent. As far as possible, non-technical language shall be used that is understandable to the subject. The background of the proposed study and the benefits and risks of the procedures and study should be explained. The subject should be provided with ample time to read the ICF and discuss it with their family and physician. The subject shall be informed that his / her participation in the clinical

investigation is confidential. The ICF must be read and understood by the subject and the subject's questions answered. The ICF must be signed and dated by both the subject and Investigator conducting informed consent prior to subject enrollment and before the subject undergoes any study-related procedures. All subjects are to receive copies of their signed and dated ICF. A copy of the approved ICF along with a copy of each patient's signed ICF will be maintained by the Investigator in a designated clinical study administrative file. Subjects may not be consented after receiving any medication that might alter their ability to comprehend the consent form (e.g. sedatives, narcotics, etc.). Study personnel should explain that even if a subject agrees to participate in the study and signs the ICF, the subject may not be eligible to participate if he / she fails to meet the screening criteria.

Written informed consent must be obtained prior to performing any protocol driven tests or any procedures that are not standard of care for a percutaneous ablation procedure that the subject is scheduled to undergo.

Once written consent has been obtained, the subject will be entered on a Screening Log, which will be maintained at each site. All subjects who provide written informed consent will be entered on the screening log regardless of whether or not they are enrolled in the study.

3.5 Study Entry Criteria

3.5.1 Inclusion Criteria

Study subjects are required to meet all the following inclusion criteria to participate in this study:

1. Patients with documented drug-resistant symptomatic persistent AF meeting all three of the following criteria:
 - a. Patient is refractory or intolerant to at least one Class I/III antiarrhythmic agent.
 - b. ECG-documented first episode of persistent AF, lasting longer than 7 days but not longer than 365 days
 - c. Holter within 90 days prior to the Enrollment Date demonstrating 24 hours of continuous AF
2. Patients who are ≥ 18 and ≤ 75 years of age on the day of enrollment.
3. Patient participation requirements:
 - a. Lives locally.
 - b. Is willing and capable of providing Informed Consent to undergo study procedures.
 - c. Is willing to participate in all examinations and follow-up visits and tests associated with this clinical study.

3.5.2 Exclusion Criteria

Subjects will be excluded from participating in this study if they meet any one of the following exclusion criteria:

1. Atrial fibrillation that is any of the following:
 - a. Paroxysmal (longest AF episode < 7 days)
 - b. Longstanding (has persisted > 12 months or that does not respond to cardioversion if < 12 months)
 - c. Secondary to electrolyte imbalance, thyroid disease, alcohol abuse or other reversible / non-cardiac causes
2. Left atrial anteroposterior diameter \geq 5.5 cm as documented by transthoracic echocardiography (TTE) or computed tomography (CT)
3. Any of the following cardiac procedures, implants or conditions:
 - a. Clinically significant arrhythmias other than AF, AFL or AT
 - b. Hemodynamically significant valvular disease
 - c. Prosthetic heart valve
 - d. NYHA Class III or IV CHF
 - e. Previous endocardial or epicardial ablation or surgery for AF
 - f. Atrial or ventricular septal defect closure
 - g. Atrial myxoma
 - h. Left atrial appendage device or occlusion
 - i. Pacemaker, implantable cardioverter defibrillator or cardiac resynchronization therapy devices
 - j. Significant or symptomatic hypotension
 - k. Bradycardia or chronotropic incompetence
 - l. History of pericarditis
 - m. History of rheumatic fever
 - n. History of congenital heart disease with any residual anatomic or conduction abnormality
4. Any of the following within 3 months prior to enrollment:
 - a. Myocardial infarction
 - b. Unstable angina
 - c. Percutaneous coronary intervention
 - d. Heart surgery (e.g. coronary artery bypass grafting, ventriculotomy, atriotomy)
 - e. Heart failure hospitalization
 - f. Stroke or TIA
 - g. Clinically significant bleeding
 - h. Pericarditis or pericardial effusion
 - i. Left atrial thrombus
5. History of blood clotting or bleeding abnormalities.
6. Contraindication to, or unwillingness to use, systemic anticoagulation.
7. Contraindications to CT or MRI.
8. Sensitivity to contrast media not controlled by premedication.
9. Women of childbearing potential who are pregnant, lactating or not using birth control.
10. Medical conditions that would prevent participation in the study, interfere with assessment or therapy, significantly raise the risk of study participation, or confound data or its interpretation, including but not limited to:

- a. Body mass index (BMI) > 40
- b. Solid organ or hematologic transplant, or currently being evaluated for an organ transplant
- c. Severe lung disease, pulmonary hypertension, or any lung disease involving abnormal blood gases or significant dyspnea
- d. Renal insufficiency with an estimated creatinine clearance < 30 mL/min/1.73 m², or any history of renal dialysis or renal transplant
- e. Active malignancy or history of treated cancer within 24 months of enrollment
- f. Clinically significant gastrointestinal problems involving the esophagus, stomach and/or untreated acid reflux
- g. Clinically significant infection
- h. Predicted life expectancy less than one year

- 11. Clinically significant psychological condition that in the investigator's opinion would prohibit the subject's ability to meet the protocol requirements.
- 12. Current or anticipated enrollment in any other clinical study.
- 13. Employment by FARAPULSE or the same hospital department or office of any investigator, or a family member of any of the preceding groups.
- 14. Use of amiodarone after day of index ablation procedure. Patients will cease use of amiodarone on or before the date of the index ablation procedure.

3.6 Enrollment

Subjects that meet all of the eligibility criteria and are deemed suitable by the investigator will be invited to participate in the study.

Subjects will be considered enrolled at the time of signing the ICF.

Each subject will be assigned a unique study identification code to protect each subject's confidential health information. The unique study identification code will not include date of birth or subject's first and last initials and will be used to link study data and other study information to the subject in lieu of the subject name. The Subject Name Log will be used to link the unique study identity code to the subject and will be maintained at the site. This log will remain confidential and will not be provided to the Sponsor, but only used for reference when monitoring at the study site.

3.7 Sample Size

Up to 40 subjects in total will be enrolled at up to four sites in this clinical safety and feasibility study. Approved sites will enroll at least 5 and not more than 20 subjects.

3.8 Investigational Sites

The clinical study will be conducted at up to four investigational sites.

3.9 Duration of Subject Participation

Subjects will be followed at 30 days, 75 days, 6 months and 12 months with a 90-day Blanking Period for recurrent atrial fibrillation, atrial flutter or atrial tachycardia following the Index Procedure.

Reablation with the study device(s) during the Blanking Period is permitted but does not extend either the Blanking Period or the total follow-up interval.

The enrollment period is estimated to take 9 months and subjects will be followed for up to 12 months for a total duration of approximately 21 months.

3.10 Subject Completion or Withdrawal

3.10.1 Study Completion

Once the subject has completed the final 12 month follow-up visit they are to be exited from the study.

3.10.2 Voluntary Withdrawal

Subjects may voluntarily withdraw from the study at any time for any reason.

3.10.3 Investigator Initiated withdrawal

The investigator may withdraw the subject due to any of the following situations:

- adverse event (AE); or
- study investigator may withdraw a patient from the study without the patient's consent if the investigator has a concern for the patient's rights, safety or welfare

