3.10.4 Documentation

At the time of study withdrawal or completion for any reason, the study exit CRF will be completed, including the reason for exit.

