3.10.5 Continuing Medical Care

Subjects leaving the study at any time will continue to receive appropriate medical care without prejudice.

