6.1 Primary Safety Endpoint

The primary safety endpoint for this study is the Composite Safety Endpoint (CSE) defined as the incidence of the following early-onset and late-onset serious adverse events (SAEs) which are device- or procedure-related, as adjudicated by the CEDMC and defined below in **Table 4. Composite Safety Endpoint Definitions**.

Early onset (within 30 days of an Index or Remap Procedure)

- Death
- Myocardial infarction (MI)
- Persistent diaphragmatic paralysis
- Stroke or transient ischemic attack (TIA)
- Peripheral or organ thromboembolism
- Pericarditis
- Cardiac tamponade / perforation
- Vascular access complications requiring intervention
- Heart block

Late onset (any time during follow-up through 12 months)

- Pulmonary vein (PV) stenosis (> 70% diameter reduction from baseline)
- Atrio-esophageal fistula

Table 4. Composite Safety Endpoint Definitions

Adverse Event	Description/Criteria
Death	Death
Myocardial infarction (MI)	Myocardial infarction will be demonstrated by any one of the following: 1) detection of ECG changes indicative of new ischemia (new ST-T wave changes or new LBB) that persist for more than 1 hour. 2) development of new pathological Q waves on an ECG 3) imaging evidence of new loss of viable myocardium or new regional wall motion abnormality
Persistent diaphragmatic paralysis	Diaphragmatic paralysis: Change from baseline diaphragmatic function as demonstrated radiographically by elevation of the diaphragm above the normal range but not due to a pulmonary process such as atelectasis. Permanent: not resolved by completion of study follow-up
Stroke or transient ischemic attack (TIA)	Stroke is an acute symptomatic episode of neurological dysfunction attributed to a vascular cause (ischemia or hemorrhage) in which symptoms last more than 24 hours, or if symptoms last less than 24 hours, a brain imaging study demonstrates infarction. Transient ischemic attack is a new focal neurological deficit with rapid symptom resolution always within 24 hours.

Adverse Event	Description/Criteria
Peripheral or organ thromboembolism	Formation in a blood vessel of a clot (thrombus) that results from the breaking loose of all or part of an existing thrombus, which is then carried by the blood to lodge in/occlude a more distal vascular site.

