7.8 Reporting

AEs and SAEs:

All AEs, including all SAEs, will be monitored from the time of enrollment through discharge for this study. All AEs must be documented in the patient chart and recorded in the appropriate CRF. A description of the event, including the start date, resolution date, action taken and the outcome shall be provided along with the Investigator's assessment of the seriousness of the event and the relationship between the AE and the study devices and/or procedures.

All AEs should be followed until the event is resolved, judged to be chronically stable or 12 month study follow-up has been completed. The investigational site will provide relevant follow-up information to the Sponsor or designee upon request.

The investigator shall also report to the Sponsor or its designee any Device Deficiencies or Malfunctions that did not but might have led to a SAE if such an event were to recur.

The investigator shall notify the Sponsor and the designated CRO immediately and not later than 24 hours after the Investigator has become aware of a **SAE or Device Deficiency / Malfunction that might have led to a SAE.**

The Investigator shall report the SAE or Device Deficiency / Malfunction on the appropriate CRF

Should mail correspondence be necessary, documents can be sent to the following:

CRO: MedPass International SAS

[contact]

Sponsor: FARAPULSE, Inc.

Email: [contact]

Contact: [name]

Return of Subject Device:

In all cases, and whenever possible the device involved in the AE, SAE, Device Deficiency / Malfunction as described above is to be returned to the Sponsor or Sponsor's designee for analysis and investigation, as appropriate. The Study Coordinator shall contact the Sponsor for instructions on returning the device.

Device Deficiencies and Malfunctions:

All Device Deficiencies / Malfunctions that did not contribute and would not likely contribute to a SAE, shall be documented on the Device Deficiency / Malfunction CRF and submitted to the Sponsor within 7 days after the observed Device Deficiency / Malfunction. The Sponsor's Quality Assurance function shall ensure an assessment is completed for each reported Device Deficiency / Malfunction. Such information shall be provided in the final clinical report.

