9.12 Study Suspension or Early Termination

The study can be discontinued at any site at the discretion of the Investigator or study Sponsor for reasons including, but not limited to, the following:

- Occurrence of adverse events unknown to date in respect to their nature, severity, or duration, or the unexpected incidence of known adverse events.
- Obtaining new scientific knowledge that shows that the study is no longer valid or necessary.
- Data demonstrates a benefit to subjects who undergo percutaneous ablation with the FARAPULSE Endocardial Multi Ablation System making treatment without the FARAPULSE Endocardial Multi Ablation System unethical.
- Insufficient recruitment of subjects.
- Unanticipated adverse device effect (UADE) presenting an unreasonable risk to subjects (Sponsor may terminate the study immediately)
- Persistent non-compliance with the Clinical Investigation Plan.
- Persistent non-compliance with regulatory requirements.

If the study is discontinued or suspended prematurely, the Sponsor shall promptly inform the clinical investigator/ investigational center of the termination or suspension and the reason(s) for discontinuation / suspension. The national and local regulatory authorities shall also be informed promptly and provided with the reason(s) for the termination or suspension by the Sponsor, CRO or by the clinical investigator/ investigation center. Further, if the study is discontinued or suspended prematurely, patients enrolled to that point will continue to be followed for safety through the 12-month timepoint.

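### A treated subject may be withdrawn from the study for any adverse event, and no safety follow-up is specified after exit, although the primary safety endpoint runs to 12 months

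*Protocol*

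**What the plan says.** Protocol 3.10.3 reads "The investigator may withdraw the subject due to any of the following situations". The first ground is "adverse event (AE); or", with no limit on severity, relatedness or timing. The second is a welfare ground, under which the "study investigator may withdraw a patient from the study without the patient's consent". Section 3.10.4 adds: "At the time of study withdrawal or completion for any reason, the study exit CRF will be completed, including the reason for exit". Section 3.10.5 adds: "Subjects leaving the study at any time will continue to receive appropriate medical care without prejudice". Nothing in 3.10 provides for safety visits, imaging or contact after an individual exit.

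Other parts of the protocol depend on later observation:

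- Section 7.8: "All AEs should be followed until the event is resolved, judged to be chronically stable or 12 month study follow-up has been completed". Withdrawal is not among the end points listed.
- Section 6.1 counts PV stenosis and atrio-esophageal fistula at any time through 12 months. For diaphragmatic paralysis, Table 4 says "Permanent: not resolved by completion of study follow-up".
- Section 9.12, on stopping the whole study: "patients enrolled to that point will continue to be followed for safety through the 12-month timepoint".

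On analysis, treated subjects stay in the Safety/ITT set (Protocol 5.6, SAP 2.3) and nothing is imputed (Protocol 5.5, SAP 2.1.2). In SAP 2.5 each component of the Composite Safety Endpoint (CSE), and the composite itself, is set to No unless a qualifying event is found, with no check on length of follow-up. The same section opens by making a derived variable missing when any item it needs is missing.

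**The concern.** The treatment is a procedure that has already been delivered. Leaving the study because of an adverse event cannot undo that exposure. Apart from any later study remapping or reablation, what ends is observation. The ground for leaving is itself a safety outcome, so the rule permits loss of safety data that is related to the endpoint being measured.

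With at most 40 subjects and few composite events to be expected, one unseen event is a visible part of the reported rate. The study is descriptive, but Protocol 5.3 says that its results will be used to design further studies.

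**Working it through.** The plan states no event-rate goal, alpha, power or dropout allowance, so there is no figure to reproduce. The check traces the rules and then bounds the effect.

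**1. Which events can be lost.** An AE that leads to exit happens before exit. Section 7.8 requires it to be recorded, 9.10 has the committee adjudicate all AEs, and SAP 2.5 derives the components from the adjudication form without reference to exit status. If it meets a component definition it can be counted. What can be lost is:

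- *PV stenosis.* The only scheduled post-index PV scan is at 75 ± 15 days (Protocol 3.12.5 and Table 3). The window opens at 75 − 15 = day 60, so an exit before then removes the scan. An exit after the scan loses no scheduled PV imaging.
- *Atrio-esophageal fistula* arising after exit.
- *Early-window events* still to come, if exit falls within 30 days of a procedure.
- *Persistence of paralysis.* For subjects with reduced phrenic response, fluoroscopy is planned at 75 days, 6 months and 12 months until resolution is shown. Table 4 does not say how to classify a subject whose status at completion of follow-up is unknown.

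Section 7.8, even if it continues after exit, covers the known AE. It does not provide for finding a new stenosis or fistula.

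**2. How the subject is scored.** Under the default code, no adjudicated event gives No, and the subject stays in the denominator. The missing-item rule could give a different answer. For example, the early-component code uses the remapping date, which a subject who exits before remap does not have; the stenosis and fistula code does not use it. The SAP does not say which rule prevails. (The SAP prints the early-window inequality in a form that, read literally, selects day 30 onward. That is a separate matter; the within-30-days meaning of 6.1 is used here.)

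**3. Size.** Let k be the number of exited subjects with a hidden event. The documents give no value, so k = 1 to 3 is assumed. N = 40 is the planned maximum; N = 25 is printed in SAP table shells 5 and 19. One hidden event is 1/40 = 2.5 points or 1/25 = 4.0 points. With no other events, the rate reported under the default code is 0%. Its Agresti-Coull upper limit (the SAP method for 0% when asymptotic assumptions fail) is 10.4% at N = 40 and 15.8% at N = 25. The worst case is k/N, with exact 95% limits:

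| N | k | Default code | Worst case | Exact 95% interval |
|---|---|---|---|---|
| 40 | 1 | 0.0% | 1/40 = 2.5% | 0.1 to 13.2% |
| 40 | 2 | 0.0% | 2/40 = 5.0% | 0.6 to 16.9% |
| 40 | 3 | 0.0% | 3/40 = 7.5% | 1.6 to 20.4% |
| 25 | 1 | 0.0% | 1/25 = 4.0% | 0.1 to 20.4% |
| 25 | 2 | 0.0% | 2/25 = 8.0% | 1.0 to 26.0% |
| 25 | 3 | 0.0% | 3/25 = 12.0% | 2.5 to 31.2% |

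Treating the exited subject as missing barely changes the result. With one event observed elsewhere and one exit at N = 40, the default code gives 1/40 = 2.5%, the missing rule gives 1/39 = 2.6%, and the worst case is 2/40 = 5.0%.

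**The case against.** The strongest reply is that the gap is narrow. Section 3.10.3 is permissive, 3.10.4 does not forbid later data, and 7.8 makes no exception for withdrawal, so the AE behind the exit can still be followed. Exit reasons are tabulated (Protocol 5.4, SAP 2.4.1), so such exits would be visible. Subjects may also leave voluntarily for any reason. The size depends on assumed exits and assumed hidden events, there is no hypothesis test, and the intervals overlap widely. All of this stands, and it limits the point.

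It also rules out several stronger readings that a reader might infer:

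- *That an injured subject is scored event-free because of the exit.* The triggering event remains countable.
- *That 7.8 demands 12 months for every AE.* It allows earlier stopping at resolution or stability. The 12-month need comes from 6.1 and the visit schedule.
- *That 9.12, or the rule in 3.11.3 keeping Therapeutic Failures in the study, contradicts 3.10.3.* Both address other situations. They show that the protocol values continued observation, no more.
- *That paralysis can never be counted after exit.* Table 4 leaves this undefined, and the SAP variable needs only an adjudicated event and dates.

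The reply does not supply post-exit surveillance for new late events, a classification for unresolved paralysis, or a settled scoring rule.

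**Conclusion.** The concern holds in limited form. An express rule permits exit on a safety outcome, and nothing provides for safety observation afterwards, while the primary safety endpoint needs that observation for its late components and for persistence of paralysis. The exposure is confined to CSE events that begin, are detected or are confirmed after exit. Whether the subject is then scored No or missing is unsettled. Either way the loss is outcome-related, and a hidden event goes uncounted.

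Each hidden event costs 2.5 points at N = 40, or 4.0 points at N = 25. The range for one to three such events is 2.5 to 7.5 points, or 4.0 to 12.0 points. These are bounds that rest on an assumed number of exits and on every exit hiding an event. They do not predict bias in this trial.

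**What to change.** **Protocol.** Reconcile 3.10.3 with 7.8, 6.1 and 9.12 so that ending study procedures because of an AE is distinct from ending safety observation. Treated subjects who have not withdrawn consent would remain in the safety assessments already scheduled through month 12. Apply the same distinction to the welfare ground in 3.10.3; otherwise the same subject could leave observation by that route. Decisions about procedures and care stay with the investigator.

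**SAP.** Replace the unconditional default to No with a stated rule for treated subjects who have incomplete follow-up and no event, and say how it relates to the missing-item rule. State how paralysis unresolved at the last observation is classified, consistently with Table 4 and the no-imputation policy. Add a worst-case sensitivity analysis of the CSE in which such subjects count as events.

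**Cost.** A short protocol amendment, a few lines in the SAP and one extra table row. The visits are already planned. The downside is slightly more follow-up for a few subjects and a possibly less favourable safety rate.
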